Liberation from Mechanical Ventilation: Each day of mechanical ventilation, all patients in the study ICU are assessed for safety of a spontaneous awakening trial (SAT) and spontaneous breathing trial (SBT)³⁶ using the SAT and SBT safety criteria from the Awakening and Breathing Controlled trial.³⁷ To prevent patients in the higher SpO₂ target group from experiencing delays in qualifying for an SBT based on receipt of higher FiO₂ to achieve the higher SpO₂ target, during the PILOT trial we will allow patients in all groups to qualify for an SAT and SBT regardless of their current FiO₂ or PEEP settings, as long as the other SAT and SBT Safety Screen criteria are met and treating clinicians feel performance of an SAT and SBT is safe. Definitions of SAT and SBT failure and the ventilator settings and duration of the SBT will not be changed from those used in the ABC trial and during usual care in the study ICU. For patients who have passed an SAT and SBT, the decision to discontinue invasive mechanical ventilation will be made by the treating clinicians.

Modification of SpO₂ Targets: At any time during the course of the study, if a treating clinician or a patient, family member, or surrogate feels an SpO₂ target other than that assigned by the study is required for the safe treatment of a specific patient, the SpO₂ target for that patient may be modified. To modify the target, the supervising physician will complete a one-page SpO₂ target modification sheet documenting the rationale for modifying the target. Details of each SpO₂ target modification will be collected and

monitored. In our prior cluster-crossover trial using the same approach to modification of therapy assignment, treating clinicians exercised the ability to modify the assigned therapy for < 5% of patients.³⁸

Anticipated examples of conditions for which treating clinicians may elect to override the assigned SpO₂ target include:

- pneumothorax
- pneumomediastinum
- carbon monoxide poisoning
- decompression sickness
- bleomycin toxicity
- paraquat toxicity

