SpO₂ Monitoring: For all mechanically ventilated patients in the study ICU, SpO₂ is continuously monitored using Nellcor™ SpO₂ Adhesive Sensors (Medtronic, Minneapolis, MN), which measure changes in red and infrared light absorption in an arteriolar bed throughout the pulse cycle to report a non-normalized real-time plethysmographic waveform and arterial hemoglobin saturation values averaged over the prior 6 seconds with a mean difference between SpO₂ and SaO₂ < 2% for SpO₂ values 80-100%.³⁹

Plethysmography and SpO₂ values are displayed [1] on IntelliVue MP90 bedside patient monitors (PHILIPS, Amsterdam, Netherlands) in each ICU room, [2] on telemetry monitors located at ICU nursing stations and adjacent to the respiratory therapy office, and [3] in real-time in the institutional EHR, available from any physical location. SpO₂ values are archived every 60 seconds into an institutional data warehouse.^{40,41} Collecting SpO₂ values every 60 seconds will allow the PILOT trial report with far greater accuracy the incidence, severity, and duration of desaturation than prior trials in which SpO₂ values were collected every 4-24 hours.^{29,30}

Feedback on SpO₂ Target Adherence: [1] During the study, the IntelliVue MP90 bedside patient monitors in each room will be set to generate an alarm for SpO₂ values outside the range considered to be at goal for the assigned SpO₂ target group. For example, for patients in the intermediate SpO₂ target group, SpO₂ values 92-96% generate no alarm, whereas SpO₂ values ≤ 91% or ≥ 97% generate an alarm alerting nursing staff and respiratory therapy to the out-of-range value. [2] Study personnel will remotely monitor SpO₂ values every four hours from 4 AM through 10 PM Monday through Friday and during a 10% sample of night and weekend hours to identify instances of lag between out of range SpO₂ values and FiO₂ titration, provide feedback and reinforcement to bedside nurses and respiratory therapists, and identify any barriers to SpO₂ target compliance. [3] Study personnel will attend respiratory therapy group meetings, nursing unit board meetings, and ICU physician leadership meetings to educate staff about the study, solicit safety concerns and adverse events, and identify and address barriers to SpO₂ target compliance. This approach to daily monitoring and

intermittent feedback to clinical personnel successfully achieved 95% compliance with the assigned intervention in a prior cluster-crossover trial in the same ICU.³⁸

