The protocol determines the SpO₂ target from enrollment until the first of: (1) discontinuation of invasive mechanical ventilation, (2) transfer out of a participating study location, (3) completion of an SpO₂ target modification sheet by treating clinicians, or (4) end of the two-month study period. The protocol does not determine the SpO₂ target during time-periods in which the patient is not physically located in a study location (e.g., during transport) or when FiO₂ is being administered for purposes other than achieving a target SpO₂ (e.g., when an FiO₂ of 1.0 is being administered for a procedure).

At any time, if a treating clinician or a patient, family member, or surrogate feels that an SpO₂ target other than that assigned by the study would be best for the optimal treatment of the patient for any reason, the SpO₂ target for that patient is modified. To modify the target, the respiratory therapist and supervising physician complete a one-

page SpO₂ target modification sheet documenting the new SpO₂ target and the rationale for modifying the target. Examples of conditions for which the assigned SpO₂ target may be modified that were specified in the initial trial protocol included: pneumothorax; pneumomediastinum; carbon monoxide poisoning; decompression sickness; bleomycin toxicity; paraquat toxicity. Examples of conditions for which the assigned SpO₂ target may be modified that were not explicitly specified in the initial trial protocol include: severe chronic obstructive pulmonary disease; severe acute respiratory distress syndrome; severe anemia; status post lung transplantation; and receipt of extracorporeal membrane oxygenation support. Trial protocol directs only the titration of FiO₂ to the assigned SpO₂ target. Other aspects of invasive mechanical ventilation, such as tidal volume [4], positive end-expiratory pressure [39,40], and use of rescue therapies for hypoxemia, are determined by institutional protocols and treating clinicians (see sections 9-17 of supplemental file 1).

Blinding

Similar to prior studies of SpO₂ targets among critically ill adults [22,24,26], patients and clinicians will not be blinded to study group assignment.

Data Collection

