3. Peak airway pressure
4. Receipt of mandatory ventilator mode
5. Number of arterial blood gasses
6. Hemoglobin
7. Red cell transfusion

21. Assessment of Compliance with the Assigned SpO₂ Target

All SpO₂ values measured during invasive mechanical ventilation are assessed for compliance with the assigned SpO₂ target. An SpO₂ value is considered compliant with the trial protocol if any of the following conditions are met:

1. Measured SpO₂ is within the target range
2. Measured SpO₂ is above the target range and the FiO₂ is 21%
3. Measured SpO₂ is below the target range and the FiO₂ is 100%
4. Measured SpO₂ occurs after treating clinicians have completed an SpO₂ target modification sheet

22. Interim Analysis

On March 23, 2020, the DSMB conducted a single, planned interim analysis for efficacy and safety at the anticipated halfway point of the trial. The interim analysis included data from patients enrolled during the first 18 months of the trial. According to the criteria specified in the trial protocol, the stopping boundary for efficacy would have been met if the P value for the difference between groups was <0.001 using a proportional odds model with independent covariates of group assignment (higher, intermediate, or lower SpO₂ target) and time. A stopping boundary for futility was not pre-specified. After conducting the planned interim analysis, the DSMB recommended the study continue without modification.

The DSMB reserves the right to stop the trial at any point, request additional data or interim analyses, or request modifications of the study protocol as required to protect patient safety.

Use of the conservative Haybittle-Peto boundary ($P < 0.001$) will allow the final analysis to be performed using an unchanged level of significance ($P = 0.05$).

23. Pre-specified Baseline Co-variates

We will repeat the primary analysis with adjustment for the following pre-specified baseline covariates: age (continuous), sex (male, female), race and ethnicity (Hispanic, Non-Hispanic Black, Non-Hispanic White, Other), source of ICU admission (ED, hospital ward, another ICU in the study hospital, operating room, outside hospital), vasopressor receipt (yes, no), and acute diagnoses at enrollment (cardiac arrest, acute myocardial infarction, sepsis or septic shock, acute respiratory distress syndrome), and severity of illness as assessed by the non-respiratory SOFA score.

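### The compliance measure in supplement section 21 scores every SpO₂ value after a target-modification sheet as compliant, so the reported percentage rises as the assigned target is replaced

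*Combined protocol and SAP*

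**What the plan says.** Supplement section 21 is headed as an assessment of compliance with the assigned SpO₂ target, and its first sentence sets the denominator: "All SpO₂ values measured during invasive mechanical ventilation are assessed for compliance with the assigned SpO₂ target". The scoring rule follows: "An SpO₂ value is considered compliant with the trial protocol if any of the following conditions are met". In short, the four criteria are:

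1. the value lies in the target range;
2. it lies above the range with FiO₂ at 21%;
3. it lies below the range with FiO₂ at 100%;
4. "Measured SpO₂ occurs after treating clinicians have completed an SpO₂ target modification sheet".

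Criterion 4 has no check against the assigned range or the new range, and no end time.

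The Oxygen Titration section of the SAP lists the events that end the protocol's control of the target. They include "completion of an SpO₂ target modification sheet by treating clinicians, or (4) end of the two-month study period". The same section states when a target is changed: if a clinician, patient, family member or surrogate feels that another target "would be best for the optimal treatment of the patient for any reason, the SpO₂ target for that patient is modified". Section 7.1 of the current protocol (version date 4/7/2021) words the threshold more narrowly, in terms of safe treatment. It gives one indication of frequency, from a prior trial of a different intervention: "treating clinicians exercised the ability to modify the assigned therapy for < 5% of patients".

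**The concern.** The section sets out to measure adherence to the assigned target. Criteria 2 and 3 fit that purpose: the value is out of range, but FiO₂ cannot be moved further toward the target. Criterion 4 differs in kind, because by then the assigned target has been replaced. Counting that time as success makes the percentage move the wrong way: the more often the assigned target is set aside, the higher the reported compliance.

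What is at stake is how an adherence percentage is read. Section 21 defines the only percentage-in-range figure in the current plan. If one arm has its target modified more often, that arm will look more adherent for that reason alone.

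**Working it through.** The documents state no compliance figure for this trial, so there is none to reproduce. The check is algebra on the definition, followed by illustrative values.

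**Notation**

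- m: share of ventilated SpO₂ values recorded after a modification sheet. Not given. The only anchor is the figure of under 5% of patients in the prior trial, taken here as 5% of values by assumption.
- c: share of the remaining values meeting criteria 1 to 3. Not given; assumed 60% to 95%.
- q: share of post-sheet values that still meet criteria 1 to 3 for the assigned target. Not given; assumed 0 to 30%. It need not be zero, since adjacent ranges share the values 92% and 96%.

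**Three ways to score the same data**

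- Section 21 as written: (1−m)c + m = c + m(1−c). The slope in m is 1−c, which is positive whenever c < 1. At m = 1 the result is 100%.
- Post-sheet values left out of numerator and denominator: c.
- All values scored on criteria 1 to 3 only: (1−m)c + mq = c − m(c−q). This falls as m rises whenever q < c.

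The excess of the section 21 figure is therefore m(1−c) over exclusion, and m(1−q) over scoring on criteria 1 to 3.

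**Values** (last column: q = 0 to q = 30%)

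| m | c | Section 21 | Post-sheet excluded | Criteria 1–3, all values |
|---|---|---|---|---|
| 5% | 60% | 62.0% | 60.0% | 57.0–58.5% |
| 5% | 80% | 81.0% | 80.0% | 76.0–77.5% |
| 5% | 95% | 95.25% | 95.0% | 90.25–91.75% |
| 20% | 60% | 68.0% | 60.0% | 48.0–54.0% |
| 20% | 80% | 84.0% | 80.0% | 64.0–70.0% |
| 20% | 95% | 96.0% | 95.0% | 76.0–82.0% |

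At m = 5%, the excess over exclusion is 0.05 × (1−0.95) = 0.25 points at c = 95% and 0.05 × (1−0.60) = 2 points at c = 60%. The excess over criteria 1 to 3 is 5(1−q) points: 5.0 at q = 0 and 3.5 at q = 30%. The 20% rows have no basis in the documents and only show how the gap grows.

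**Comparison between arms.** Take two arms with c = 80%, one with m = 5% and one with m = 20%. Section 21 gives 81% and 84%. Criteria 1 to 3 over all values give 76.0–77.5% and 64–70%. The order is reversed.

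**The case against.** The strongest defence is that the scoring sentence speaks of compliance with the trial protocol. The protocol permits modification and gives up control of the target once a sheet is completed, so a value recorded afterwards cannot breach it. That is right as far as it goes, but it justifies removing those values from the measure, not counting them as successes. Nor is the credit applied consistently. The SAP names other points at which the protocol stops determining the target: transfer out of a study location, the end of the two-month period, and FiO₂ given for a procedure. Section 21 gives automatic credit to none of them.

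Other parts of the defence stand, and they rule out stronger readings that a reader might infer:

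- **That the primary result is biased.** It is not. The main analysis is intention-to-treat and does not use compliance.
- **That a null result could not be told from failure to deliver the contrast.** Supplement section 20 lists SpO₂, SaO₂, FiO₂, PaO₂ and the hypoxemia and hyperoxemia episodes as measures of separation, with no exception for modified patients. Loss of contrast would show there. Compliance has no stated analytic role, and the documents do not say where it will be reported.
- **That all post-sheet time is non-compliant.** Scoring it so gives c(1−m), or 57% at c = 60% and m = 5%. That is a lower bound (q = 0), since some post-sheet values may lie in the assigned range.
- **That the arms differ in modification.** No rates by arm are given, so this is conditional.
- **That the prior trial's 95% shows the problem.** Section 7.1 of the protocol says its monitoring approach "successfully achieved 95% compliance with the assigned intervention in a prior cluster-crossover trial in the same ICU". That trial tested a different intervention. Its figure did not come from criterion 4 and is not a projection for this one.

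**Conclusion.** The point holds as a defect in a descriptive statistic. Under section 21 the reported percentage rises with the share of post-sheet values whenever c is below 100%, and it is not comparable across arms if modification differs by arm. No other part of the plan corrects this.

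The size cannot be fixed from the documents. It is small if about 5% of values follow a sheet, as the working shows, and that share is itself an assumption. The documents' figure counts patients, not values, and comes from another intervention. Patients ventilated for longer contribute more values, and the SAP's threshold for modification is broad, so the share of values could be larger. The claim that true adherence falls as m rises also needs q < c. This is a minor point, worth correcting because the correction is cheap.

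**What to change.** Remove criterion 4 from section 21 and report, by arm:

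- (a) the share of all ventilated SpO₂ values meeting criteria 1 to 3 for the assigned target, with post-sheet values scored on the same criteria as the rest;
- (b) the same share with post-sheet values excluded from the denominator;
- (c) the number of patients, and the share of ventilated time, under a modified target.

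Figure (a) describes adherence to the assigned target, (b) describes adherence while the protocol's target had not been modified, and (c) lets a reader see why the two differ.

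The cost is a small programming change. Supplement section 18 already records the date, time, new range and rationale of each modification, and section 6 archives SpO₂ every 60 seconds. The compliance figure becomes slightly less favourable if modification is rare. No clinical rule changes.

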Communication with DSMB members will be primarily through the DSMB Chair and the primary investigator ([name]) or study biostatistician ([name]). Study investigators will not communicate about the study with DSMB members outside of DSMB meetings. The primary investigator may contact the DSMB Chair when needed for urgent concerns or clarifications of recommendations.

4. DSMB Members and Research Staff

DSMB members and their expertise are listed in Appendix A. The DSMB Chair will perform the functions of the Executive Secretary (ES). He will draft meeting summaries, compose final recommendations, and assure the accurate and timely transmission of the final recommendations to the investigators. The primary investigator ([name]) will be responsible for timely notification of co-investigators of all DSMB recommendations. *Ad hoc* members may be added to supplement expertise for single or multiple meetings.

5. Scheduling, Timing, and Organization of Meetings

DSMB meetings will be held by teleconference. The purpose of the first meeting is to review and discuss this Charter, provide an overview of study activities, review the trial protocol, review the DSMB data reporting template, and finalize the Data and Safety Monitoring Plan. Each DSMB member will sign and return this Charter to the primary investigator ([name]) to

indicate recommendation for approval. Enrollment in the trial will not begin until the DSMB has recommended approval and IRB approval has been obtained.

- Meetings by teleconference will be held twice a year, with additional meetings scheduled as needed. Conference calls will be scheduled by the primary investigator ([name]) in collaboration with the DSMB members.
- A single interim analysis will be performed in the 30 days after data on the primary outcome is available for patients enrolled in the first 18 months of the trial.
- The DSMB will conclude its operations when all study procedures, follow up, analysis, and publication of the primary results have been completed.

The agenda for DSMB meetings will be drafted by the primary investigator ([name]) and study biostatistician ([name]), and finalized in consultation with the DSMB Chair. The agenda and meeting materials will be distributed by the primary investigator ([name]) or his appointee, two (2) weeks before each meeting. The NHLBI Program Office will receive this material at the same time as DSMB members.

When the agenda is distributed, DSMB members will be asked to report any new conflicts of interest since the last DSMB meeting. New conflicts will be reviewed by the Chair and study staff to determine if the conflict limits the ability of the DSMB member to participate in the discussion according to conflict of interest policy at the study institution.

To ensure proper trial conduct, at each meeting the DSMB will review the following data:

- adverse events and other safety data,
- quality and completeness of study data, and
- enrollment data

At the single pre-planned interim analysis after 18 months of enrollment, the DSMB will review a formal interim analysis for efficacy by the primary endpoint (*as outlined below in the stopping guidelines*).

It is expected that all DSMB members will attend every meeting. For the purposes of voting on recommendations, a quorum is three (3) members of the Board. All standing Monitoring Board members are voting members. The Board may also decide in advance whether *ad hoc* members can vote.

6. Organization of Meetings

Meetings are organized into open, closed, and executive sessions.

- **Open session** - information is presented to the DSMB by the study investigators, with time for discussion.
- **Closed session** - the DSMB and blinded study staff (NHLBI program staff may be invited to attend at the Chair's discretion) discuss confidential data (any study data grouped by treatment arm), including information on efficacy and safety. The DSMB can decide to be unblinded to treatment assignments by the study statistician. The principal investigator and staff involved in subject enrollment and treatment may not be present or review grouped data.

- **Executive session** (optional) DSMB members (and NHLBI program staff at the Chair's discretion) may elect to convene to discuss study issues independently. If the executive session occurs on a conference call, steps will be taken to ensure that only the appropriate participants are on the call, and to invite others to re-join the call only at the conclusion of the executive session.
- **Recommendations** (optional) – Meeting attendees may be reconvened to receive the DSMB's recommendations.

At the conclusion of the closed and executive sessions, the participants will be re-convened so that the DSMB Chair can provide a summary of the DSMB's recommendations. This provides an opportunity for study investigators to ask questions to clarify the recommendations. The meeting is then adjourned.

7. Expedited Safety Reporting

A system has been established to track and report adverse events (AEs). Study personnel will monitor the safety of subjects and follow AEs until the event resolves or is explained.

Clinical Outcomes (not considered Adverse Events). In this study of critically ill patients who are at high risk for death or other adverse outcomes due to their underlying critical illness, clinical outcomes, including death and organ dysfunction, will be systematically tracked (collected in the case report form) and will be included as part of the analyses for this study. For the purposes of reporting, death and organ dysfunction will not be recorded as AEs unless the investigator believes the event may have been caused by the study or is more severe or prolonged than expected given the underlying critical illness. Listed below are events that will be tracked as primary or secondary clinical outcomes and will not therefore be reported as AEs (unless believed to be study related and more severe or prolonged than expected given the underlying critical illness):

1. Death (all deaths occurring prior to hospital discharge will be reported on the CRF in the vital status at hospital discharge section);
2. Recurrence of respiratory failure, including need for re-intubation or non-invasive mechanical ventilation, presence of acute respiratory distress syndrome, or presence of pneumothorax;
3. Circulatory failure, including cardiac arrest or shock with or without receipt of vasopressors;
4. Incidence of sustained atrial and ventricular arrhythmias;
5. Acute kidney injury, including leading to increased creatinine or receipt of renal replacement therapy;
6. Hepatic injury or failure leading to increased bilirubin, AST, or ALT;
7. Coagulation derangements leading to elevated PT/INR or PTT, DIC, thrombocytopenia, or thrombocytosis;
8. Lactic acidosis;
9. Delirium, disability, and physical or cognitive impairment believed to be newly acquired;
10. All values for SpO₂, SaO₂, FiO₂, PaO₂, or PaO₂/FiO₂ ratio;
11. All values for vital signs (e.g., temperature, respiratory rate, SpO₂);
12. Receipt of co-interventions (e.g., net fluid balance, number of arterial blood gasses, red cell transfusion)
13. Duration of ICU admission, ICU readmission;

14. Duration of hospitalization, hospital readmission;
15. Alterations in routine labs, including chemistries, complete blood counts, liver function tests, and hemostasis profiles.

Adverse Event Classifications. An Adverse Event (AE) will be defined as any untoward medical occurrence for a patient enrolled in the trial that is not tracked as a clinical outcome, regardless of whether the event is considered study related or not. All AEs occurring during the observational study period will be recorded on the CRF. All AEs will then be assessed as to whether they are (1) related to study procedures, (2) serious, and/or (3) unexpected according to the following definitions:

- I. **Related to study procedures.** AEs that the investigator suspects are related to the study will be classified as study related. Certainty of relatedness is not required as long as a reasonable possibility exists that the AE is related to a study procedure.
- II. **Serious.** AEs that meet any of the criteria below will be considered Serious Adverse Events (SAEs):
 - a. Results in death
 - b. Is life-threatening (defined as an event in which the participant was at risk of death at the time of the event and NOT an event that hypothetically might have caused death if it would have been more severe)
 - c. Prolongs an existing hospitalization
 - d. Results in persistent or significant disability or incapacity
 - e. Results in a congenital anomaly or birth defect
 - f. Important medical event that requires an intervention to prevent any of a-e above.
- III. **Unexpected.** AEs that are more severe or prolonged than expected based on the investigator's discretion will be considered Unexpected.

Communication and Reporting of Adverse Events. AEs will be recorded in the AE CRF in the electronic database and reported to the primary investigator ([name]) within 5 calendar days of occurrence. The primary investigator will provide a report of all AEs annually to the IRB, and semi-annually to the DSMB as part of the semi-annual DSMB meetings. All SAEs will be reported to the primary investigator within 72 hours of occurrence. The primary investigator will, in turn, report all SAEs to the IRB, DSMB, and funding body within 7 calendar days of occurrence. Consistent with NHLBI policy, unanticipated problems that do not qualify as an SAE will be reported by the investigator to the IRB, DSMB, and NHLBI within 14 calendar days of the investigator becoming aware of the problem.

Review by the DSMB. All AEs will be reviewed by the DSMB at the scheduled semi-annual DSMB meetings. All SAEs will be reviewed by the DSMB Chair within three (3) days of notification. The DSMB Chair will respond to the primary investigator ([name]) and NHLBI program office with recommendations within seven (7) days.

8. Reports to the DSMB

For each meeting, the study biostatistician ([name]) will prepare summary reports and tables to facilitate the oversight role of the DSMB. The DSMB will discuss at the first and subsequent meetings what data they wish to review and how it should be presented (Appendix B).

9. Reports of DSMB Deliberations

- **Full Summary and Recommendations:** The DSMB Chair/ES is responsible for sending the DSMB meeting summary to the Board within seven (7) calendar days of the meeting. The summary should be signed by the DSMB Chair and include key topics discussed, the response of the investigators to previous recommendations, and the recommendations of the DSMB. The study statistician may receive the full summary as decided by the DSMB chair on a meeting by meeting basis.

Voting on recommendations will follow Roberts' Rules of Order (**Robert's Rules of Order Newly Revised (11th Edition) RONR**).

- **Board Recommendations** - signed by the DSMB Chair, will be sent to the investigators within fourteen (14) calendar days after the meeting. Recommendations should include a statement as to whether the study is approved to continue as planned, should continue with specified changes, or should be stopped. Requests for additional data from the investigators or DCC/statistician should include an expected due date. In addition to recommendations memos issued to investigators (for review and IRB distribution), recommendations related to blinded data or data analysis issues may be issued separately for DCCs or statisticians.

The recommendations will be distributed by the principal investigator to co-investigators, to the local IRB, and to the NHLBI Program Office.

- **Action plan:** This lists the DSMB's recommendations and the primary investigator's action plan outlining the steps required to implement the DSMB recommendations. It is submitted to the NHLBI Program Office and DSMB within fourteen (14) calendar days after the DSMB meeting.

10. Statistical Monitoring Guidelines

In addition to ongoing monitoring of safety throughout the trial, the DSMB will conduct a single interim analysis for efficacy and safety at the anticipated halfway point of the trial. The interim analysis will include patients enrolled during the first 18 months of the trial. The stopping boundary for efficacy will be met if the P value for the difference between groups is <0.001 using a proportional odds mixed effects model accounting for fixed effects (group) and random effects (period) with regard to the primary outcome of VFDs. Use of the conservative Haybittle-Peto boundary ($P < 0.001$) will allow the final analysis to be performed using an unchanged level of significance ($P = 0.05$). There will be no stopping boundary for futility. The DSMB will reserve the right to stop the trial at any point, request additional data or interim analyses, or request modifications of the study protocol as required to protect patient safety. If the 18-month interim analysis reveals an enrollment indicative of $<80\%$ statistical power at completion, we will ask the DSMB to approve extending enrollment of the study to ensure the trial is not underpowered to detect the planned difference between groups in the primary outcome.

PILOT Trial Statistical Analysis Plan Revision Sequence

April 2, 2021	Original Statistical Analysis Plan completed
April 5, 2021	Original Statistical Analysis Plan submitted for publication
August 25, 2021	Statistical Analysis Plan submission completed peer review
August 31, 2021	Final patient enrolled
October 28, 2021	Final Statistical Analysis Plan* published: [name], [name], [name], [name], [name], [name], [name], [name], [name], [name], [name], [name], [name], [name], [name], [name]; PILOT Investigators and the Pragmatic Critical Care Research Group. Protocol and statistical analysis plan for the Pragmatic Investigation of optimal Oxygen Targets (PILOT) clinical trial. BMJ Open . 2021 Oct 28;11(10):e052013. PMID: 34711597

**No changes to content of the statistical analysis plan occurred between submission of the Protocol and Statistical Analysis Plan and its publication.*
